## 6 Statistical methods for Pharmacokinetic (PK) parameters

All subjects within the PK analysis set will be included in the PK data analysis.

### 6.1 Variables

The following PK parameters will be determined, if data permit, using the actual recorded sampling times and non-compartmental method(s) with Phoenix WinNonlin (Version 8.0 or higher), from the plasma concentration-time data:

AUCtau	The area under the plasma concentration-time curve calculated to the end of the dosing interval (tau) at steady-state (h*ng/ml)
AUClast	The area under the plasma concentration-time curve calculated to the last measurable concentration sampling time (tlast) (h*ng/ml)
Cmax	The observed maximum plasma concentration (ng/ml)
Ctrough (Cmin)	The concentration observed just prior to the beginning, or at the end, of a dosing interval (ng/mL)
Tmax	The time to reach maximum plasma concentration (h)
T1/2 (if feasible)	The elimination half-life associated with the terminal slope (lambda_z) of a semi-logarithmic concentration-time curve (h)

### 6.2 Descriptive analyses

LNP023 plasma concentrations will be listed by sequence, treatment dose group, patient, and visit/sampling time point. Summary tables will be presented as described in [Section 4](#).

Commercially Confidential Information

Comercially Confidential Information

Pharmacokinetic parameters will be listed by patient and summarized by treatment with descriptive statistics as listed above. For Tmax, only median, minimum, and maximum will be reported. For T1/2 geometric means will not be calculated.

Graphical methods will be employed to show mean (SD) with time defined as the sampling time point by treatment dose group on linear and semi-log view based on nominal time.

Moreover, individual PK values trough levels up to Week 12 will be displayed. In addition, all individual concentration-time profiles will be displayed graphically by treatment dose and sequence (in separate plots), visit/sampling time point on linear and semi-log view based on nominal time.

### **6.3 Statistical model, assumptions and hypotheses**

Modeling techniques will be applied on the PK parameters (AUCtau, AUClast and Cmax) at Period Week 4 (i.e. including data from both Period 1 Week 4 and Period 2 Week 4).

In the first instance a mixed model will be fitted with log transformed PK parameter as the dependent variable and dose as a categorical variable, and subject as a random term to give predicted estimates per each dose. The subject term will be considered as random so as to allow recovery of between subject information. The results of the treatment effects will be presented as geometric means by back-transforming estimates from the log scale and will be presented along with a 95% confidence interval.

Comercially Confidential Information

#### **6.3.1 Model checking procedures**

Comercially Confidential Information

#### **6.3.2 Graphical presentation of results**

The model predicted relationship curve between dose and PK parameter along with its corresponding 95% CI will be presented for the nonlinear model.

## 7 Statistical methods for Pharmacodynamic (PD) parameters

All subjects within the PD analysis set will be included in the PD data analysis.

### 7.1 Primary objective

The primary objective is to assess the effect of LNP023 on the reduction of PNH associated hemolysis.

#### 7.1.1 Variables

The primary variable is treatment response. A responder is defined as a patient with at least 60% reduction in LDH compared to baseline or LDH below upper limit of normal (ULN) at any time up to and including Week 12 for that patient, whether or not CCI , and a non-responder anyone who doesn't meet either of these criteria.

Baseline LDH will be calculated as the average of the last three screening values prior to randomization.

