At least 10 patients will be included in the study, as replacement can occur if any patient withdraws for reasons unrelated to safety or lack of efficacy.

Active hemolysis is defined by an LDH value \geq 1.5x ULN. At least 3 pre-treatment LDH measurements each separated by at least a week over a maximum of 8 weeks prior to study Day 1 of the study should be \geq 1.5x ULN, in order to include the patients in the study. LDH medical history data can be taken into consideration for inclusion purposes but at least one value must be from the study central laboratory. If medical history data is not available, the screening period may consist of several visits for LDH verification.

Total study duration from screening until EOS is approximately 28 months. This three-period study includes:

- a screening phase of up to 8 weeks,
- a baseline visit,
- Day 1 (first day that the investigational drug is given),
- a 4-week treatment period of LNP023 at the first dose in the assigned sequence (Period 1),
- an 8-week treatment period at the second dose in the assigned sequence (Period 2),
- an approximately 2 year treatment extension period for patients who respond to the LNP023 treatment (Period 3)
- taper down period of 2 weeks applicable only for patients discontinuing LNP023 treatment (Week 13 for non-responders or Week 109 for responders).

Commercially Confidential Information

- an EoS visit that will take place 1 week after the last LNP023 administration for patients not joining the roll-over extension program (REP). For patients joining the REP ([Section 9.2](#)), the last treatment visit will become the EoS visit.

A safety follow-up call 30 days after the last administration of LNP023 will be performed for patients not joining the REP.

Figure 3-1 Study design

Commercially Confidential Information

Patients will be randomized to sequence 1 or sequence 2 in ratio 1:1.

Commercially Confidential Information

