Subjects who meet the eligibility criteria at screening will continue to randomization and baseline evaluations. All baseline safety evaluation results must be available prior to randomization and dosing (note: local LDH levels are acceptable for the purpose of confirming eligibility prior to randomization). Local laboratories may be used to confirm eligibility of the patient at baseline, however, all baseline samples should also be sent to central laboratory for analysis. Baseline visits can be conducted on the same day as the last screening visit, in case the last screening visit is not more than 7 days prior to Day 1. All baseline assessments need to be performed at this time.

Pharmacokinetic, safety and other study assessments will be conducted according to the study schedule (see corresponding sections). Safety assessments will include physical examinations, ECGs, vital signs, standard clinical laboratory evaluations (hematology, blood chemistry, and urinalysis), adverse event and serious adverse event monitoring.

All patients need to complete vaccinations against *N. meningitidis*, *S. pneumoniae* and *H. influenzae* at least 4 weeks prior to starting LNP023 treatment. After initial immunization, booster doses of the vaccinations should be administered according to the label of the vaccination used. The screening period may be extended to allow vaccination procedures to be completed. This is applicable for vaccinations only and all the other screening assessments should be performed within the period described in the [Assessment Schedule](#). However, if LNP023 treatment has to start earlier than 4 weeks post-vaccination, prophylactic antibiotic treatment must be initiated ([Section 6.6.2](#)). In addition, to reduce risk of infection, antibiotics will be required for patients with any sign of infection.

Body temperature should be measured daily in Period 1 and Period 2 and at minimum at the time of symptoms of infection during treatment Period 3. A diary will be completed by the patient to record, amongst other data, elevation of body temperature on days when no study visit is planned. The investigator shall review diaries at every visit. Patients will be instructed

to contact their physician immediately if body temperature rises to $>38.3^{\circ}\text{C}$. For details, please refer to [Section 6.6.2](#).

Please refer to the [Assessment Schedule](#) for details regarding assessments to be performed.

4 Rationale

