5.1 Inclusion criteria

Subjects eligible for inclusion in this study must meet **all** of the following criteria:

1. Written informed consent must be obtained before any assessment is performed.
2. Male and female patients at least 18 years old at baseline.
3. Diagnosis of active PNH based on documented clone size of $\geq 10\%$ by RBCs and/or granulocytes, measured by GPI-deficiency on flow cytometry (screening or medical history data acceptable).

4. LDH values $\geq 1.5 \times$ upper limit of the normal range (ULN) for at least 3 measurements over a maximum of 8 weeks prior to Day 1 (Screening, baseline or medical history data acceptable).
5. Hemoglobin level $< 10.5 \text{ g/dL}$ at Baseline.
6. For Period 3 of the study, patients who as per judgment of Investigator benefit from LNP023 treatment based on reduced hemolytic parameters as compared to Screening and Baseline.
7. Vaccinations against *N. meningitidis*, *S. pneumoniae* and *H. influenzae* is required at least 4 weeks prior to first dosing with LNP023 (existing vaccinations should provide effective titers at time of LNP023 treatment start). If LNP023 treatment has to start earlier than 4 weeks post vaccination, prophylactic antibiotic treatment must be initiated.
8. Able to communicate well with the investigator, to understand and comply with the requirements of the study.

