8.3 Efficacy/Pharmacodynamics

8.3.1 LDH measurement

Serum LDH is a measure for intravascular hemolysis and is usually elevated in PNH patients. In order to help characterize disease status and progression, historical values of serum LDH prior to the informed consent signature (if available), may be recorded in the eCRF as part of the medical history assessment and to verify inclusion/exclusion criteria. The blockade of complement mediated lysis of erythrocytes is expected to result in reduction of serum LDH levels. LDH measured as a part of the study will be determined in serum by a validated assay. Detailed methodological description of the assay will be included in the bioanalytical data report. Please refer to [Assessment Schedule](#) for time points when clinical chemistry is analyzed. All the LDH values and local normal ranges collected during screening should be recorded in

the CRF. If available as a part of the patients' medical history, at least the 5 most recent LDH values recorded prior to screening visit should be recorded in the CRF in order to characterize the pre-treatment LDH profile over time.

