12.5 Analysis of secondary endpoints

Assessment of plasma pharmacokinetics is a secondary endpoint but the analyses for it are described below in [Section 12.5.3](#). Assessing the dose-response effect on LDH and other parameters associated with PNH associated hemolysis is the first secondary objective.

Mixed effect modelling will be performed for LDH.

Commercially Confidential Information

Commercially Confidential Information

Baseline LDH will be calculated as the average of the last three screening values prior to randomization. The subject term will be considered as random so as to allow recovery of between subject information.

Commercially Confidential Information

The same mixed modelling approach will be used for other key continuous response secondary endpoint variables apart from LDH that are markers of intravascular and extravascular hemolysis, or are markers of thrombosis, as well as for PK parameters excluding Tmax (see [Section 12.5.3](#)). In these cases, except for PK parameters, the baseline covariate is the average of all pre-treatment values.

Data may be transformed in order to meet underlying normality and homoscedasticity assumptions. In case early escalation gives data only to two weeks for some patients, the modelling will be adjusted to suit, in the first instance looking only at Week 2 data for all patients.

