### **7.2.1 Variables**

The secondary variables of this study are:

- For dose response: LDH, and other relevant parameters including but not restricted to hemoglobin and red blood cell count
- Markers of intravascular and extravascular hemolysis CCI  
Including but not restricted to total and free hemoglobin, carboxyhemoglobin, reticulocytes, C3 fragment deposition, haptoglobin, bilirubin, red blood cell count, platelet counts, ferritin, PNH type III red blood cells (RBC) and PNH clone size
- Risk of thrombosis parameters: Including but not limited to, fibrinogen, prothrombin time, activated partial thromboplastin time, thrombin time, fibrin D-dimer and fibrinogen degradation products for fibrinolysis activity.

Baseline LDH will be calculated as the average of the last three screening values prior to randomization. For all parameters except LDH, baseline is the average of all pre-treatment values.

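### Does the baseline LDH rule need redefining because it names no laboratory and leaves out the Day 1 pre-dose value?

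*SAP*

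**What the plan says.** A patient responds if LDH falls by at least 60% from baseline, or drops below ULN, at any time up to Week 12 (Protocol 12.4.1, SAP 7.1.1). SAP 7.1.1 defines the baseline: "Baseline LDH will be calculated as the average of the last three screening values prior to randomization". Protocol 12.5 and SAP 7.2.1 repeat this. Other parameters follow a different rule. SAP 7.2.1 has "For all parameters except LDH, baseline is the average of all pre-treatment values", and Protocol 12.5 has "except for PK parameters, the baseline covariate is the average of all pre-treatment values".

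The text on where LDH values come from is spread over several sections:

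- Protocol 5.1, criterion 4, requires raised LDH "for at least 3 measurements over a maximum of 8 weeks prior to Day 1 (Screening, baseline or medical history data acceptable").
- Protocol Section 3 adds that these values lie at least a week apart, and that "LDH medical history data can be taken into consideration for inclusion purposes but at least one value must be from the study central laboratory". If there is no history, screening may run over several visits to verify LDH.
- Section 3 also says that "local LDH levels are acceptable for the purpose of confirming eligibility prior to randomization", and that "all baseline samples should also be sent to central laboratory for analysis".
- Protocol 8.3.1 says that "LDH measured as a part of the study will be determined in serum by a validated assay". It asks sites to record screening LDH with local normal ranges.
- Table 8-1 schedules chemistry, which includes LDH (Protocol 8.4.1.1), at Screening (Days -56 to -4), Baseline (Days -3 to -1) and Day 1 before the dose.

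**The concern.** Baseline LDH is the denominator of one of the two routes to response, and the visible rule can be read in two ways.

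- **Narrow reading.** Only values from screening visits count. A patient who qualified on medical history may then have a single screening value, and no visible rule covers fewer than three.
- **Wide reading.** The three values that established eligibility count. Every patient then has three, but two of them may be local or historical, while on-treatment LDH comes from the study assay.

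Both readings leave out the Day 1 pre-dose sample, and the narrow one also leaves out the Baseline visit. Other parameters use all pre-treatment values, and the visible text gives no reason for treating LDH differently. The primary endpoint is a count with a bar of 5 in 10, so one patient whose status depends on which values are averaged could decide the result. The natural suggestion is to average all central values through Day 1 instead.

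**Working it through.** The documents give no within-patient CV for LDH and no local-to-central ratio. Both are assumptions below.

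**1. The plan's own figure.** Protocol 12.8.1 gives 80% for 5 or more responders of 10 at a true rate of 58%. The binomial sum over x = 5 to 10 of C(10,x) × 0.58^x × 0.42^(10-x) is 0.798. The figure is right, and the baseline rule does not enter it.

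**2. Who can be affected.** The 60% route is easier than LDH below ULN only if 0.4 × baseline > ULN, that is, baseline > 2.5 x ULN. Entry requires 1.5 x ULN. Below 2.5, an unbiased baseline has no effect on status. Above it, only patients whose best fall is near 60% are affected.

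**3. Wide reading: bias.** Let two of three values be local, with local/central ratio r. The averaged baseline is f = (2r + 1)/3 times the central one, and the central fall needed is 1 - 0.4f.

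| r (assumed) | f | Central fall needed | Baseline above which the 60% route matters (2.5/f) |
|---|---|---|---|
| 0.8 | 0.867 | 65.3% | 2.88 x ULN |
| 0.9 | 0.933 | 62.7% | 2.68 x ULN |
| 1.0 | 1.000 | 60.0% | 2.50 x ULN |
| 1.1 | 1.067 | 57.3% | 2.34 x ULN |
| 1.2 | 1.133 | 54.7% | 2.21 x ULN |

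Status changes only for a patient whose best fall lies between 60% and the shifted line.

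**4. Narrow reading: random error in baseline only.** With n independent values, SE = CV/√n. If the lowest on-treatment LDH is held fixed, the chance of falling on the wrong side for a true fall F is 1 - Φ(|(1 - F)/0.4 - 1|/SE). For F = 55% or 65% the numerator is 0.125.

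| CV (assumed) | n = 1 | n = 2 | n = 3 |
|---|---|---|---|
| 20% | 26.6% | 18.8% | 14.0% |
| 10% | 10.6% | 3.9% | 1.5% |

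Taken alone, this favours having more baseline values.

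**5. The same error on treatment.** The endpoint takes the best of about 10 post-dose chemistry visits to Week 12, so the lowest value is not fixed. Let each visit read (1 - F)(1 + CV × Z) independently around a constant level. A patient responds if the minimum is at or below 0.4(1 + SE × Z0). Simulated false response at F = 55%:

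| CV | Visits | One baseline value | Three baseline values |
|---|---|---|---|
| 20% | 10 | 82% | 90% |
| 20% | 6 | 74% | 81% |
| 10% | 10 | 65% | 70% |

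The apparent gain from step 4 reverses. The lowest of many readings sits well below the true level, so an average-sized baseline already yields a response. Mostly it is a low-reading baseline that prevents one, and averaging makes those rarer. This does not mean that fewer values are better in general. At F = 65%, CV 20% and 10 visits, the same model gives a missed response in 3.8% with one value and 0.4% with three. The direction depends on the true fall.

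**6. The suggested replacement.** Central values at Screening, Baseline and Day 1 give three values, the last two only days apart. With correlation 0.8 between those two (assumed) and CV 20%, the variance of the mean is CV² × (3 + 2 × 0.8)/9, so SE = 14.3%. The step 4 formula gives 1 - Φ(0.125/0.143) = 19.1%. If Screening and Baseline coincide, as Table 8-1 allows, only two values remain. Then SE = 20% × √((2 + 2 × 0.8)/4) = 19.0% and the chance is 25.5%. Three independent values give 14.0%, and the eligibility values, at least a week apart, are closer to that.

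**The case for a change.** The strongest case is that a programmer cannot apply the rule uniquely. Criterion 4 treats screening, baseline and history as separate sources, Table 8-1 has one Screening column, and extra screening visits are optional. A central Baseline sample shows that better data exist but does not put them in the average. One patient can matter: at a true rate of 58%, exactly 4 responders has probability 13.0% and exactly 5 has 21.6%. The same baseline also feeds the LDH dose-response model.

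It stands that the visible text names no laboratory, does not settle whether Baseline-visit values count, and has no rule for fewer than three. The rest is weaker:

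- Section 3 ties historical and local LDH to eligibility. Nothing visible assigns them to the baseline, so the wide reading needs a step that the plan does not take.
- The Screening column spans more than seven weeks, and repeat visits are foreseen for patients without history. A single-value baseline can arise only for those who qualify on history, and their number is unknown.
- Text is redacted directly after the missing-value rules (Protocol 12.4.3, SAP 7.1.2.1), throughout Protocol 12.5.1 and in most of SAP Section 4. A laboratory or missing-value rule would sit there.
- Stopping at randomization is a choice stated alike in all three places. A different rule for other parameters does not contradict it.

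**Conclusion.** No change follows. The point is a detail that the visible text leaves unwritten and that analysts would fill sensibly, from study LDH drawn before randomization, with local and historical results kept for eligibility. The shift to between 54.7% and 65.3% in the required fall rests on an assumed 20% laboratory bias in two of three values. It reaches only patients with a baseline above roughly 2.2 to 2.9 x ULN and a best fall near the line. The precision argument depends on holding the on-treatment minimum fixed. With measurement error on treatment as well, its direction depends on the true fall. Under the stated assumptions, the replacement could be less precise than three spaced values (19.1% or 25.5% against 14.0%).

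Moving to a new primary baseline also has a price. The study is open-label, and Protocol 9.2 reports that benefit has already been observed in it, so a prespecified definition should not be exchanged without a demonstrated gain. The study is non-confirmatory, the primary endpoint carries no test, and the 80% in Protocol 12.8.1 is unaffected.

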#### 7.1.2 Descriptive analyses

Frequency tabulations reporting number and percentage of responders by week 12 by randomized sequence. Frequency tables will also be summarized by dose over time as described in [Section 4](#).

There is no statistical model for the primary endpoint apart from observing and counting success or failure for each patient. For the purposes of this study a positive sign of efficacy is when the estimated response rate is at least 50%. For example, this criterion will be met when at least 5 out of 10 patients in the overall study, or 3 of 5 in one of the two Cohorts are considered responders.

#### 7.1.2.1 Handling of missing values/censoring/discontinuations

For calculation of the success rate for the primary endpoint all patients enrolled in the study apart from those who were replaced for reasons other than safety or efficacy will be included in the denominator.

Commercially Confidential Information

### 7.2 Secondary objectives

The secondary objectives of this study are:

- To assess the dose-response effect of LNP023 on the reduction of PNH associated hemolysis.
- To assess the effect of LNP023 on markers of intravascular and extravascular hemolysis.
- To assess the effect of LNP023 on markers associated with risk of thrombosis

### **7.2.1 Variables**

The secondary variables of this study are:

- For dose response: LDH, and other relevant parameters including but not restricted to hemoglobin and red blood cell count
- Markers of intravascular and extravascular hemolysis CCI  
Including but not restricted to total and free hemoglobin, carboxyhemoglobin, reticulocytes, C3 fragment deposition, haptoglobin, bilirubin, red blood cell count, platelet counts, ferritin, PNH type III red blood cells (RBC) and PNH clone size
- Risk of thrombosis parameters: Including but not limited to, fibrinogen, prothrombin time, activated partial thromboplastin time, thrombin time, fibrin D-dimer and fibrinogen degradation products for fibrinolysis activity.

Baseline LDH will be calculated as the average of the last three screening values prior to randomization. For all parameters except LDH, baseline is the average of all pre-treatment values.

#### **Partial exclusion of data**

In case of an INCL05 deviation, all total and free hemoglobin records from the patient will be excluded from the PD analyses.

